6.3.1. Hypoglycemic Events

Specific criteria for monitoring hypoglycemic events have been designed to ensure subject safety and to closely monitor hypoglycemia.

At each visit through the end-of-treatment visit (Visit 9; Week 26), subjects should be trained on the signs and symptoms of hypoglycemia (e.g., hunger, confusion, dizziness, anxiety, increased heart rate, visual disturbances), including nocturnal hypoglycemia (i.e.,

nightmares; night sweats; tired, irritable, or confused upon awakening), as well as the common causes of hypoglycemia. Subjects should also be educated on appropriate methods to help prevent hypoglycemia (i.e., strictly observe nutritional guidance from the physician or study site staff, consume small snacks before intense exercise, promptly communicate with the study site on “ill days” for additional guidance). It is also particularly important to advise subjects to contact the study site before any potential dietary change, as this may necessitate a change in insulin doses to avoid the development of hypoglycemia. Subjects should also be educated on how to treat hypoglycemia (e.g., oral glucose treatment with simple carbohydrates).

Subjects will be asked to report hypoglycemic events that occur between study visits using a diary. In this study, hypoglycemic events are defined according to recommendations by the American Diabetes Association and The Endocrine Society Workgroup on Hypoglycemia [Sequist, 2013]. To aid correct classification and treatment of hypoglycemic events, subjects should be instructed to repeat SMBG measurements ≤ 70 mg/dL (≤ 3.9 mmol/L).

Severe Hypoglycemia

- Severe hypoglycemia is an event requiring assistance of another person to actively administer carbohydrates, glucagon, or take other corrective actions. Plasma glucose concentrations may not be available during an event, but neurological recovery following the return of plasma glucose to normal is considered sufficient evidence that the event was induced by a low plasma glucose concentration

Documented Symptomatic Hypoglycemia

- Documented symptomatic hypoglycemia is an event during which typical symptoms of hypoglycemia are accompanied by a measured plasma glucose concentration ≤ 70 mg/dL (≤ 3.9 mmol/L)

Asymptomatic Hypoglycemia

- Asymptomatic hypoglycemia is an event not accompanied by typical symptoms of hypoglycemia but with a measured plasma glucose concentration ≤ 70 mg/dL (≤ 3.9 mmol/L)

Probable Symptomatic Hypoglycemia

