- Probable symptomatic hypoglycemia is an event during which symptoms typical of hypoglycemia are not accompanied by a plasma glucose determination but that was presumably caused by a plasma glucose concentration ≤ 70 mg/dL (≤ 3.9 mmol/L)

Pseudohypoglycemia

- Pseudohypoglycemia is an event during which the person with diabetes reports any of the typical symptoms of hypoglycemia with a measured plasma glucose concentration >70 mg/dL (>3.9 mmol/L) but approaching that level

Importantly, any report by a subject in the eDiary of a hypoglycemic event should be assessed and classified by the investigator per the above definitions, and recorded as a non-serious or serious adverse event if appropriate.

Any hypoglycemic event, regardless of intensity, that satisfies the definition of an SAE (Section 6.3.7.2) should be categorized as outlined in this section and reported appropriately in the SAE eCRF page.

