6.3.7.1. Definition of an AE

Any untoward medical occurrence in a patient or clinical investigation subject, temporally associated with the use of a medicinal product, whether or not considered related to the medicinal product.

Note: An AE can therefore be any unfavorable and unintended sign (including an abnormal laboratory finding), symptom, or disease (new or exacerbated) temporally associated with the use of a medicinal product. For marketed medicinal products, this also includes failure to produce expected benefits (i.e., lack of efficacy), abuse or misuse.

Events meeting the definition of an AE include:

- Exacerbation of a chronic or intermittent pre-existing condition including either an increase in frequency and/or intensity of the condition
- New conditions detected or diagnosed after study treatment administration even though it may have been present prior to the start of the study
- Signs, symptoms, or the clinical sequelae of a suspected interaction
- Signs, symptoms, or the clinical sequelae of a suspected overdose of either study treatment or a concomitant medication (overdose per se will not be reported as an AE/SAE) unless this is an intentional overdose taken with possible suicidal/self-harming intent. This should be reported regardless of sequelae.

“Lack of efficacy” or “failure of expected pharmacological action” per se will not be reported as an AE or SAE. However, the signs and symptoms and/or clinical sequelae resulting from lack of efficacy will be reported if they fulfil the definition of an AE or SAE.

Events that **do not** meet the definition of an AE include:

- Medical or surgical procedure (e.g., endoscopy, appendectomy); the condition that leads to the procedure is an AE
- Situations where an untoward medical occurrence did not occur (social and/or convenience admission to a hospital)
- Anticipated day-to-day fluctuations of pre-existing disease(s) or condition(s) present or detected at the start of the study that do not worsen
- The disease/disorder being studied, or expected progression, signs, or symptoms of the disease/disorder being studied, unless more severe than expected for the subject's condition

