8.3.5.1. Hypoglycemic Events

Hypoglycemic events merit special attention in the development and study of drugs for the treatment of T2DM since they are often related to the efficacy of a compound. In order to accomplish this, hypoglycemic event data including supplemental hypoglycemic event information not collected on AE eCRF page are reported on a separate hypoglycemic event eCRF page. However, any hypoglycemic event that meets the criteria for a serious AE will also be included in the serious AE summaries.

Analysis of on-therapy hypoglycemic events will include all AEs coded to the preferred term of 'Hypoglycemia'. For on-therapy hypoglycemic events the number and percentage of subjects with events, the number of events, the incidence rate (per 100 person-years) and AE density (per 100 person-years) by the severity of the event defined by American Diabetes Association [ADA], SAE status, relationship to the investigational product, and withdrawal status will be summarized by treatment group. The events will also be summarized according to intervention provided, action taken with regard to background and anti-hyperglycemic medications and onset week and glucose levels. All hypoglycemic events will be classified as severe, documented symptomatic,

asymptomatic, probable symptomatic, or pseudohypoglycemia per the American Diabetes Association criteria) criteria.

The number of events of hypoglycemia with confirmed home blood glucose monitoring < 3.9 mmol/L and/or requiring third party intervention (i.e., severe, documented symptomatic and asymptomatic hypoglycemic events) in 3 monthly intervals (i.e., from Baseline to Week 12, >Week 12 to Week 26) will be summarized by treatment group. The exposure-adjusted event rate will be compared between treatment groups using a Poisson regression model with offset for the person-year, which will include HbA_{1c} stratum, age (<65 years versus ≥65 years), current use of metformin (metformin use versus no metformin use), and region as covariates.

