Incidence (in total and by each category) of hypoglycemia, daytime hypoglycemia, and nocturnal hypoglycemia will be summarized by treatment group. Daytime hypoglycemia is defined as hypoglycemic events with an onset between 06:00 hours and 00.00 hours (inclusive). Nocturnal hypoglycemia is defined as hypoglycemic events with an onset between 00:01 hour and 05:59 hours (inclusive). The incidence of hypoglycemia with blood glucose <56 mg/dL (<3.1 mmol/L), regardless of symptoms, will also be summarized by treatment group.

On-therapy hypoglycemic events over time will be summarized by onset week and plotted for each treatment group.

A by-subject listing of all hypoglycemic events will be produced.

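### The SAP picks on-therapy hypoglycemic events by one AE preferred term, so an event that meets a protocol 6.3.1 category can be left out of the on-therapy hypoglycemia analyses

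*SAP*

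**What the plan says.** Protocol 6.3.1 sets the event categories. "Severe hypoglycemia is an event requiring assistance of another person to actively administer carbohydrates, glucagon, or take other corrective actions"; a glucose value is not required. "Documented symptomatic hypoglycemia is an event during which typical symptoms of hypoglycemia are accompanied by a measured plasma glucose concentration" at or below 70 mg/dL (3.9 mmol/L). "Asymptomatic hypoglycemia is an event not accompanied by typical symptoms of hypoglycemia but with a measured plasma glucose concentration" at or below the same threshold. Every diary report is to be assessed and classified by the investigator under these definitions, and "recorded as a non-serious or serious adverse event if appropriate".

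Protocol 8.3.5.2 says hypoglycemic events are analyzed apart from other AEs and classified into the 6.3.1 categories. It names no preferred term.

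SAP 8.3.5.1 first describes the data source: "hypoglycemic event data including supplemental hypoglycemic event information not collected on AE eCRF page are reported on a separate hypoglycemic event eCRF page". It then states the selection rule: "Analysis of on-therapy hypoglycemic events will include all AEs coded to the preferred term of" Hypoglycemia. The summaries by category, intervention and glucose level follow, together with the Poisson comparison of event rates. SAP 2.1, which lists changes from the protocol's analysis, does not mention a preferred-term filter.

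**The concern.** The plan has two ways of deciding what a hypoglycemic event is, and they need not give the same set. The protocol uses clinical and glucose criteria applied to each reported event. The SAP uses presence on the AE page together with one coded term. No rule says what happens to an event that satisfies the first and not the second.

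Less hypoglycemia is one of the expected benefits in the protocol rationale and a key secondary objective. The trial is open-label. Protocol 5.3 relies on an objective laboratory endpoint to limit bias, and that does not protect a count that depends on an investigator deciding whether to make an AE entry. If entry practice differed between arms, the on-therapy rates would not be comparable.

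**Working it through.** No figure in either document tests this point, so the check is a comparison of texts, followed by a short illustration on stated assumptions.

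**Path of an event.** Under protocol 6.3.1 and SAP 8.3.5.1 an event passes through these steps:

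1. The subject reports it in the diary.
2. The investigator classifies it under 6.3.1. This applies to every report.
3. It is entered as an AE or SAE, if judged appropriate. This step is conditional.
4. The term is coded in MedDRA.
5. It enters the on-therapy hypoglycemia analysis if coded to Hypoglycemia.

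The protocol's categories are settled at step 2. The SAP selects at step 5. The difference is whatever is lost at steps 3 and 4.

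**Step 3.** The wording of 6.3.1 foresees classified events with no AE entry. The SAP does not say that an event held only on the hypoglycemic event page is counted, and no reconciliation of the two pages is described.

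**Step 4.** An episode entered by its manifestation, or as a laboratory finding, could code to a different term.

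**Exposure by category.**
- Severe events are the least exposed. Protocol 6.3.1 requires any hypoglycemic event that satisfies the SAE definition to be categorized and reported on the SAE page, and SAP 8.3.5.1 puts it in the SAE summaries. That still does not place it in the hypoglycemia tables if it is coded elsewhere.
- Asymptomatic lows are the most exposed. A symptom-free reading of 65 mg/dL meets the definition, but an investigator could reasonably see no need for an AE entry.

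**Reach of the rule.** It governs the on-therapy hypoglycemia displays in SAP Appendix 14 (Tables 3.71 to 3.80), including the exposure-adjusted rate analyses (3.76 to 3.79). The key secondary endpoint (SAP 8.1.2.2) and the composites (8.1.3.6, 8.2.8) repeat no preferred-term filter, but they name no data source either.

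**Comparison within the SAP.** For systemic allergic reactions (8.3.5.6), liver events (8.3.5.8) and pneumonia (8.3.5.10), the SAP summarizes events reported by the investigator on the eCRF and adds a customized query or a list of terms. Hypoglycemia has the narrower rule.

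**Illustration.** Let c_L and c_A be the fractions of true events captured in the lispro and albiglutide arms. Then

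observed rate ratio (lispro to albiglutide) = true ratio × c_L / c_A.

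The protocol rationale cites about 1.5- to 2-fold less symptomatic hypoglycemia with albiglutide in earlier studies. The capture fractions below are assumptions with no source in the documents.
- Equal capture: the ratio is unchanged, and both rates are understated by the same proportion.
- c_L = 0.90, c_A = 0.80: 1.5 × 0.90/0.80 = 1.69; 2 × 0.90/0.80 = 2.25.
- c_L = 0.80, c_A = 0.90: 1.5 × 0.80/0.90 = 1.33; 2 × 0.80/0.90 = 1.78.

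The error can run either way, and nothing in the documents says which.

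**The case against.** The strongest reply is that hypoglycemic events are plainly meant to be AEs, so the filter loses little. Protocol 6.3.9 lists them first among the AEs of special interest, with eCRF pages that capture additional details. Protocol Table 1 calls hypoglycemia the most common adverse effect of insulin. SAP 5.5 and Appendix 4 speak of AEs as including hypoglycemic events, and SAP 8.3.2 removes them from most AE summaries, which presupposes that they are in the AE data. The selection sentence says the analysis will include such AEs, not that it is limited to them. The text that follows classifies all hypoglycemic events. Protocol 5.1.3.3 alerts investigators to meter readings at or below 50 and between 50 and 60 mg/dL, which covers essentially every reading below 56.

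Most of this stands, and it rules out some stronger readings.

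- A reader might infer that the protocol's AE rules keep lows off the AE page, because 6.3.7.1 lists as not being AEs "The disease/disorder being studied, or expected progression, signs, or symptoms of the disease/disorder being studied, unless more severe than expected" for the subject, and 6.3.8 has a similar rule for safety assessments. Neither names hypoglycemia. The disease under study is type 2 diabetes, and the protocol treats hypoglycemia as an effect of treatment.
- A reader might infer that the incidence below 56 mg/dL regardless of symptoms has to be derived from meter records. The protocol chose subject-reported, investigator-classified events, and the alerts make it likely that the investigator knows of these lows. A meter-derived version is a matter of preference.

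What the reply does not answer is the conditional AE entry in 6.3.1. An alert or a page for additional details does not by itself create an AE coded to one particular term. A programmer who follows the only stated selection rule would have grounds to leave out an event without that code.

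**Conclusion.** The point holds as a gap in specification: the SAP does not ensure that every event meeting a 6.3.1 category enters the on-therapy hypoglycemia tables and Poisson comparisons. It rests on a literal reading of the selection sentence and on the conditional AE entry in the protocol. If every event on the hypoglycemic event page is in practice also an AE coded to Hypoglycemia, nothing is lost. The documents neither require that nor check it.

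The size and direction of any loss cannot be determined, because no capture rate or event count is given. Two further inferences should be avoided. One is that events are being lost, or lost in a way that favors albiglutide; the text shows only that they could be. The other is that the key secondary endpoint is subject to the filter; SAP 8.1.2.2 defines it by category without one, and what it lacks is a stated source.

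**What to change.** In SAP 8.3.5.1, replace the preferred-term rule. Include all on-therapy events on the hypoglycemic event eCRF page, whatever their preferred term and whether or not they are also on the AE page, plus any SAE that meets the severe definition in protocol 6.3.1. Classify all of them by 6.3.1 category.

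Reconcile the hypoglycemic event page with the AE and SAE pages before database lock. Name the same source in SAP 8.1.2.2 for the key secondary endpoint and in the sections on the composites that involve hypoglycemia (8.1.3.6 and 8.2.8).

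The change uses data already collected. It costs a small amount of programming and reconciliation, and counts of mild events may rise in both arms.

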
 To evaluate the safety and tolerability of the 2 treatment groups 	
 Adverse events (AEs) and serious AEs (SAEs), including AEs and SAEs leading to discontinuation of randomized study medication Other AEs of special interest (for example, cardiovascular [CV] events, GI events, injection site reactions, potential systemic allergic reactions, pancreatitis, pancreatic cancer, medullary thyroid cancer, malignant neoplasms following treatment with insulin, diabetic retinopathy events, appendicitis, liver events, pneumonia, and atrial fibrillation/flutter) Assessments of hypoglycemia: 
 Percentage and number of events of hypoglycemia with confirmed home blood glucose monitoring and/or third-party intervention through Week 26 (i.e., severe, documented symptomatic, and asymptomatic hypoglycemic events, see Section 6.3.1) in 3-month intervals (i.e., from Baseline/Randomization to Week 12, >Week 12 to Week 26) Incidence of hypoglycemic events (in total and by each category as defined by the American Diabetes Association criteria) Incidence of daytime hypoglycemia (in total and by category), defined as hypoglycemic events with an onset between 06:00 hours and 00:00 hours (inclusive), and nocturnal hypoglycemia (in total and by category), defined as hypoglycemic events with an onset between 00:01 hours and 05:59 hours (inclusive) Incidence of hypoglycemia with blood glucose <56 mg/dL (<3.1 mmol/L), regardless of symptoms Assessment of clinical laboratory tests (hematology, clinical chemistry, urinalysis, β-human chorionic gonadotropin [β-HCG], lipid panel) Assessment of vital sign measurements (Note: Weight is assessed as part of

Objective	Endpoint
	efficacy), 12-lead electrocardiogram (ECG) findings, and physical examination findings
Exploratory	

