8.3.3.2. Other Comparisons of Interest

A key secondary endpoint is the proportion of subjects treated with once-weekly albiglutide that are able to replace prandial insulin without the need for re-introduction of insulin lispro. The 95% confidence interval of the sample proportion will be estimated, stratified by region, age category, and current use of metformin.

The proportion of subjects with hypoglycemia, as confirmed by plasma glucose monitoring <70 mg/dL (<3.9 mmol/L) and/or requiring third-party intervention through Week 26, will be compared between treatment groups, adjusting for baseline HbA_{1c} stratum, age group, current use of metformin, and region.

Other binary secondary endpoints, such as the proportion of subjects achieving HbA_{1c} treatment goals at Week 26 and the proportion of subjects achieving composite secondary endpoints (i.e., criteria involving HbA_{1c} target and hypoglycemia) will be analyzed analogous to the proportion of subjects with hypoglycemia.

Continuous secondary endpoints, e.g., changes over time in HbA_{1c}, FPG, and body weight, changes in daily insulin dose, changes in mean daily blood glucose based on 8-point SMBG, and changes in total number of weekly insulin injections will be summarized descriptively and analyzed using an MMRM (observed data). In the MMRM for non-HbA_{1c} endpoints, the corresponding baseline variable will be modeled as a covariate (in place of baseline HbA_{1c}) for variance reduction and to adjust for any baseline differences in treatment groups attributable to chance as well as the randomization stratification variables (HbA_{1c} stratum, age category, current use of metformin).

The number of hypoglycemic events with confirmed home blood glucose monitoring <70 mg/dL (<3.9 mmol/L) and/or requiring third-party intervention in 3-month intervals (i.e., from Baseline/Randomization to Week 12, >Week 12 to Week 26) will be compared between the treatment groups using a Poisson regression model with offset for the person-year, which will include treatment effect and covariates such as HbA_{1c} stratum, age (<65 years versus ≥65 years), current use of metformin (metformin use versus no metformin use), and region.

The time to meeting prespecified criteria for severe, persistent hyperglycemia at Week 26 will be analyzed for treatment group differences using pairwise log-rank tests within a Kaplan-Meier model.

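### The confirmed-hypoglycemia count uses a strict cut-off (<3.9 mmol/L, <70 mg/dL) but is equated with event classes that Protocol 6.3.1 defines inclusively (≤3.9 mmol/L, ≤70 mg/dL)

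*SAP*

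**What the plan says.** **Class definitions (Protocol 6.3.1).** "Documented symptomatic hypoglycemia is an event during which typical symptoms of hypoglycemia are accompanied by a measured plasma glucose concentration" of ≤70 mg/dL (≤3.9 mmol/L). For the next class the limit is again ≤70 mg/dL (≤3.9 mmol/L), worded as follows: "Asymptomatic hypoglycemia is an event not accompanied by typical symptoms of hypoglycemia but with a measured plasma glucose concentration". Severe events are defined by the need for help from another person, whatever the glucose value. The class on the other side of the line starts only above 70 mg/dL (3.9 mmol/L). The protocol describes it thus: "Pseudohypoglycemia is an event during which the person with diabetes reports any of the typical symptoms of hypoglycemia with a measured plasma glucose" value over that limit.

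**Endpoint (Protocol 2, repeated in SAP 2.2).** The confirmed-event assessment in 3-month intervals is described as "severe, documented symptomatic, and asymptomatic hypoglycemic events, see Section 6.3.1".

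**Analysis in the SAP (8.3.5.1).** The quantity analyzed is introduced as "The number of events of hypoglycemia with confirmed home blood glucose monitoring < 3.9". The same sentence then gives the unit, the third-party route and the classes it takes these events to be: "mmol/L and/or requiring third party intervention (i.e., severe, documented symptomatic and asymptomatic hypoglycemic events". The counts are summarized by 3-month interval. The next sentence compares the exposure-adjusted event rate by Poisson regression. The title of Table 3.75 repeats <3.9 mmol/L.

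**Analysis in the protocol (8.3.3.2).** The proportion of subjects with hypoglycemia is compared "as confirmed by plasma glucose monitoring <70 mg/dL (<3.9 mmol/L) and/or requiring third-party intervention through Week 26". The Poisson analysis of the number of events uses the same strict limit.

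The SAP's list of changes from the protocol (2.1) does not mention the cut-off.

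**The concern.** SAP 8.3.5.1 gives two descriptions of one analysis set and says that they are the same. One is a numeric filter that excludes the threshold value. The other is a list of three classes, two of which include it. For a non-severe event at exactly the threshold, both cannot be followed.

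What is at stake is consistency between displays. Table 3.75 carries the strict limit in its title. Table 3.76 covers the same three classes and Tables 3.77 to 3.79 cover each class singly, all with no limit stated. A programmer working from the titles could produce a 3-month count and a modelled rate that are presented as the same events but are not. Less hypoglycemia is one of the expected advantages of the albiglutide regimen, so unexplained differences between its tables would be unwelcome.

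**Working it through.** No sample size, power, alpha or event count in the documents depends on this cut-off, so there is no stated figure to reproduce. The check is to set the rules side by side and apply them to readings near the threshold.

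**1. Which rule applies where**

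| Place | Rule |
|---|---|
| Protocol 6.3.1, documented symptomatic and asymptomatic | ≤70 mg/dL (≤3.9 mmol/L) |
| Protocol 6.3.1, pseudohypoglycemia | >70 mg/dL (>3.9 mmol/L) |
| Protocol 8.3.3.2, proportion of subjects | <70 mg/dL (<3.9 mmol/L) |
| Protocol 8.3.3.2, number of events (Poisson) | <70 mg/dL (<3.9 mmol/L) |
| SAP 8.3.5.1, number of events | <3.9 mmol/L |
| SAP Table 3.75, title | <3.9 mmol/L |
| SAP Tables 3.76 to 3.79, titles | by class, no limit stated |
| SAP 8.1.2.2, key secondary endpoint | by class, no limit stated |

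**2. What each rule does with a reading.** The mmol/L value is the mg/dL value divided by a conversion factor. The documents give no factor, so 18.0 to 18.0182 is assumed.

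| Reading as held in the data | Inclusive rule | Strict rule |
|---|---|---|
| 70, in mg/dL | counted | not counted |
| 3.9, in mmol/L | counted | not counted |
| 70 mg/dL converted, unrounded: 70/18.0182 = 3.885 to 70/18.0 = 3.889 | counted | counted |
| 70 mg/dL converted, rounded to 3.9 | counted | not counted |
| 71 mg/dL converted, unrounded: 3.9405 to 3.944 | not counted | not counted |
| 71 mg/dL converted, rounded to 3.9 | counted | not counted |

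The two rules disagree at the threshold except when a 70 mg/dL reading is held as an unrounded mmol/L value. The last row shows that changing the inequality alone is not enough. On rounded mmol/L data, ≤3.9 would admit 71 mg/dL, which Section 6.3.1 places above the limit.

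**3. Which events can be lost.** An event that needed third-party intervention is counted at any glucose value. Only documented symptomatic and asymptomatic events exactly at the threshold are exposed.

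**4. How many.** The documents give neither a glucose distribution nor the resolution of the meter, so the number cannot be computed. As an illustration only, suppose that qualifying readings are spread evenly over n steps up to the threshold. The share in the top step is then 1/n.

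- Steps of 1 mg/dL, lower end 40: n = 70 − 40 + 1 = 31, share 3.2%. Lower end 60: n = 11, share 9.1%.
- Steps of 0.1 mmol/L, lower end 2.2: n = (3.9 − 2.2)/0.1 + 1 = 18, share 5.6%. Lower end 3.3: n = 7, share 14.3%.

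The even spread, the lower ends and the step sizes are all assumptions. The figures are not estimates for this trial.

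**The case against.** The strongest reply is that nothing need be lost. Protocol 6.3.1 has the investigator classify each reported event, and SAP 8.3.5.1 says that all hypoglycemic events will be classified in this way. The endpoint refers back to Section 6.3.1, and the explanatory clause in the SAP names the classes as the analysis set. The example Poisson code in SAP Appendix 11 shows no glucose filter. On this reading the strict sign is loose wording. Events are also tabulated by glucose level (Table 3.73) and listed by subject, so threshold events stay visible.

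Much of this stands. Loss is conditional on programming the printed inequality. But the inequality appears in two sentences of the protocol, one of the SAP and one table title, and the example code models an event count that it does not define. The documents do not say which description governs.

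Four stronger readings are tempting and are not supported:

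- *The modelled rates in Table 3.76 will be wrong.* That table is titled by class. Only Table 3.75 carries the strict limit, so disagreement between the two is possible but not certain.
- *The key secondary hypoglycemia result is affected.* SAP 8.1.2.2 defines it as severe or documented symptomatic hypoglycemia, with no strict limit. The written test order in SAP Appendix 10 does not list hypoglycemia. The accompanying diagram shows a percentage-of-subjects endpoint whose label is cut off in the available text. If that is this endpoint, it is still defined by class.
- *The comparison is biased towards one arm.* The same rule applies to both arms, and nothing in the documents indicates a direction.
- *A large share of events sits on the boundary because meters report in 0.1 mmol/L steps.* Neither the meter resolution nor the distribution is given.

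**Conclusion.** The point holds as a contradiction in how one planned analysis is specified. A cut-off that excludes the threshold is declared equal to classes that include it, and the SAP does not record this as a deliberate change. Applied as printed, it omits non-severe events at exactly 70 mg/dL or 3.9 mmol/L from the 3-month counts in Table 3.75 and possibly from the Poisson model, while the class-based displays keep them.

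The consequence is small. It is confined to non-severe events exactly at the limit, depends on the stored unit and rounding, and touches no alpha-controlled test, sample size or primary conclusion. The number of events and any effect on the treatment comparison cannot be determined from the documents. This is a low-priority correction, worth making because it costs almost nothing.

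**What to change.** In SAP 8.3.5.1, the title of Table 3.75 and both analyses in Protocol 8.3.3.2, define the analysis set as the severe, documented symptomatic and asymptomatic classes of Protocol 6.3.1. Equivalently, replace the strict limits with ≤70 mg/dL (≤3.9 mmol/L), keeping the third-party route for severe events. State that the cut-off is applied in the unit originally recorded, before any conversion or rounding. This keeps a 70 mg/dL reading in and a 71 mg/dL reading out. Define the event-count variable in the example Poisson code in the same terms, so that Tables 3.75 and 3.76 draw on one set.

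The cost is a few words in the SAP, one table title and two sentences in the protocol. No new data are needed, and sample size and alpha are unchanged. If the protocol is not to be amended for this alone, an entry in SAP 2.1 would record the alignment.
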